5.3 Additional Guidance regarding specific diets

Patients can be enrolled in CHIP even if a physician has suggested that they eat one of the following diets. These patients will be encouraged to replace their current diet with CHIP:

- Mediterranean
- DASH
- MIND
- Atkins
- South Beach

- Keto
- Low carb
- High protein (unless for malnutrition or a specific health condition relating to nutritional deficiencies)
- Other diets targeting diabetes, obesity, or metabolic syndrome.

Diets we are able to accommodate (i.e. they can be on both a CHIP diet and this diet at once):

- Gluten free (celiac)
- Kosher (patient can decline to eat our pre-prepared food but would be able to make kosher food at home consistent with CHIP)
- Halal (patient can decline to eat our pre-prepared food but would be able to make halal food at home consistent with CHIP)
- Vegetarian
- Vegan
- Taking communion (alcohol is not encouraged on CHIP, but we will not discourage wine with communion)
- Coffee and tea drinkers
- Low sodium
- Low oxalate (e.g. for kidney stones)
- Food allergies.

Diets that we are not able to accommodate (patients will be excluded):

- Phenylketonuria (PKU)
- Any malabsorption or malnutrition diet except for a gluten-free diet for celiac
- Feeding tube of any sort
- Low vitamin K due to warfarin therapy
- Low potassium.

Any diets not covered in the above guidance will be assessed at the discretion of the study medical director, with any necessary input from the Lifestyle Medicine Institute team, according to the following criteria:

- Is the CHIP diet safe for this patient?
- Could this patient participate meaningfully in the CHIP dietary intervention?

5.4 Recruitment

Members meeting the above criteria will be invited via direct mail, MyGeisinger messages or phone to participate in this study. Potential participants will be asked complete the pre-screening questionnaire to confirm that they meet the study's inclusion and exclusion criteria. Potential

participants meeting the study criteria will be asked to review an electronic consent form. A link to the electronic consent form may be sent to those that are interested by email with permission from the potential participant. Study staff will be available by phone to answer any questions that participants may have while reviewing the electronic consent form. After consent is obtained, participants will be randomized 1:1 to either the control or intervention arm based on their most recent HbA1c on file with GHP. The reasons for any potential subjects' exclusion from the study will be tracked by the study team.

5.5 Study Duration

5.5.1 Approximate Duration of Subject Participation

Subjects will participate in the study for approximately 6 months. This includes the enrollment followed by 12 weeks of active intervention, as well as follow-up for 14 weeks post-intervention completion to include biometric, biomarker, and psychometric assessments.

5.5.2 Approximate Duration of Study

This pilot study will be completed in approximately 15 months. The end of the study will be the collection and completion of data analysis for all study data. The fifteen-month duration accounts for recruitment and start-up, 12-week intervention period, an additional 14-week biometric/biomarker measurement period, a 3-month lag in claims data processing, and a 3-month electronic data retrieval and analysis period.

5.6 Procedures

The CHIP intervention arm will be modeled after Vanderbilt's version of CHIP with adjustments made to fit the needs of GHP members and current logistical limitations related to COVID-19 (Shurney, et al., 2013). The CHIP curriculum will be administered during twice weekly 1-hour classes over a 6-week period, followed by weekly 1-hour classes for an additional 6 weeks. The protocol will begin with a 1-month in-person period, with participants subsequently offered the choice between in-person and online attendance for the remaining sessions. The protocol will be flexible with contingencies for inclement weather and any necessary social distancing related to the COVID-19 pandemic. Online classes will be conducted by the facilitators from the Miller Center over a HIPAA-compliant Microsoft Teams application.

Facilitators

Facilitators will be existing employees of Evangelical Community Hospital Health and Wellness. They will undergo CHIP facilitator training through the Lifestyle Medicine Institute's online program.

Intervention

GHP members randomized to the intervention arm will participate in the following:

- Attend 2 group meetings per week over 6 weeks, followed by one group meeting per week for 6 weeks (12 weeks total); meetings will be held in the evening and last approximately one to two hours. Meetings include:
 - Educational materials presented through a small group interactive lecture format based on the standard CHIP curriculum, including topics such as diet, sleep, exercise instruction, stress management, and toxic substance avoidance. The educational portion lasts approximately one hour.
 - Ten meetings will include a cooking demonstration and partaking in a meal prepared in the Cornerstone Kitchen according to The Optimal Diet, The Official CHIP Cookbook. Online participants will be encouraged to prepare the recipes at home. The group meal will last approximately one hour.
- Receive a copy of The Optimal Diet, The Official CHIP Cookbook.
- Receive access to online resources through CHIPHub.
- Participate in virtual meetings should in-person meetings be restricted.
 - Participants will be sent the menu for meals associated with all sessions at the start of the class. When participants cannot attend due to pandemic restrictions, or if they choose to attend a meeting virtually, they will be encouraged to buy their own ingredients and prepare the same meal they would have been served on site at the Miller Center. Participants will be encouraged to prepare the meal before the class, post photographs and communicate via discussion board and/or video chat. The meeting can include discussion of participants' experience cooking.
 - The same interactive lectures used for in-person meetings will be used for virtual meetings.

Additional procedures for the hybrid online/in-person approach will be as follows:

- Participants will be asked to enroll only if they can make a good faith effort to attend at least 80% of classes live (in-person or online) and to watch classes they miss within one week of the live event
- Participants will be expected to attend in person at the Miller Center twice weekly for the first month, practicing appropriate social distancing measures as may be necessary at the time of this event. After the first month, they will have the option of attending either in-person at the Miller Center or over Microsoft Teams for all subsequent classes except for the final class.
- All classes can be moved to a mandatory online format in case of inclement weather and/or if current public health recommendations preclude in-person classes from being held. The facilitators will lead all classes from meeting spaces at the Miller Center. This decision to alter format due to weather or pandemic concerns will be made at the discretion of the Miller Center director
- Participants will be disenrolled from the program if they request to be removed from the study (e.g. if they withdraw consent, if they move out of the area). The study doctor could decide to disenroll participants from this research study if they believe it is in the participant's best interest, if a participant had two consecutive HbA1c results less than 6.5% while off all diabetes medications, if a participant does not follow the study direction, if a participant is not able to attend the required classes, or for any other reason

- Participants in the intervention group will be compensated up to \$150. Participants will receive a \$25 check for each completed blood draw at weeks 1, 12 and 26. They will also receive a \$25 check for each month that they complete at least 75% of the required CHIP classes.

We feel this is adequate reimbursement for participants' time and travel at these timepoints.

Participants will receive their checks in the mail up to 8 weeks after they are issued. In order for checks to be issued, participants will be asked to complete a W-9 form. This form will include participants name, address, and Social Security Number.

Data Collection

A study team member will attend the first CHIP session at the Miller Center and the last session to collect biometrics, biomarkers and psychometrics. Study samples (biomarkers) may also be collected at a Geisinger lab. All participants will also be scheduled for 6-month appointments with the research phlebotomist or at a Geisinger lab. The following data will be collected:

- Biometrics: Weight, BMI, Waist circumference, Systolic and diastolic blood pressure
- Biomarkers (blood tests): HbA1c, LDL-C
- Psychometrics: Wellbeing360 survey
- Current medication list

Data collection protocols will be as follows:

- Biometric, biomarker, and medication data will be collected by the study team at the Miller Center or biomarkers may be collected at a Geisinger lab. Baseline appointments will be offered before and after the first scheduled class and 3-month data collection will occur the week of the final class. Data collection at 6-months will occur at appointments scheduled individually with participants. Participants will complete the Wellbeing360 survey through CHIPHub. They will be given as much time as they need to complete the survey. Study staff will make up to three reminder calls to participants around the time they are due for each survey to encourage them to complete the surveys and assist with any technical difficulties. Data will be uploaded to the Lifestyle Medicine Institute's HIPAA-compliant servers, with the raw data transferred to secure Geisinger servers within one week. Medication lists will be determined based upon a medication reconciliation process which will begin by asking each participant what medication he or she takes. If a participant is not confident of his or her medication list, a study team member will obtain the medication list from the patient's primary care office and/or review the patient's chart in Epic to confirm medication list accuracy. The study team will obtain permission to access medication information for patients who are not seen within the Geisinger system. For participant with complex medication lists, or those which for any reason cannot be reconciled/entered into the database within the span of a standard biometric/biomarker appointment, the study team will prioritize collection of biomarkers and biometrics during the in-person encounter, as these need to be collected in-person and are especially time sensitive. For medication reconciliation and data entry

which requires more time with the participant, or guidance from the study physician, a study team member will follow up over the phone.

- Control arm subjects will have the same measures collected with the same protocols at the Miller Center at private appointments at baseline, 3-months and 6-months and the biomarkers for the control group may also be collected at a Geisinger lab.

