5.7 Primary Endpoints

Clinical endpoint: Change in HbA1c at 6 months compared to baseline.

Feasibility endpoint: What proportion of individuals contacted agree to participate; what proportion of participants complete the intervention; what proportion of individuals contacted are excluded from the study based on lack of access to transportation or internet.

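### In the CHIP arm, weight, waist and blood pressure are collected around class sessions at baseline and 3 months but at individual appointments at 6 months; controls have private appointments throughout, so the 6-month comparison could carry a setting effect

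*Combined protocol and SAP*

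**What the plan says.** Section 5.6 (Data Collection) describes CHIP-arm collection twice. The overview reads: "A study team member will attend the first CHIP session at the Miller Center and the last session to collect biometrics, biomarkers and psychometrics". The detailed text that follows reads: "Baseline appointments will be offered before and after the first scheduled class and 3-month data collection will occur the week of the final class". For the last visit it says: "Data collection at 6-months will occur at appointments scheduled individually with participants".

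For the other arm it says: "Control arm subjects will have the same measures collected with the same protocols at the Miller Center at private appointments at baseline, 3-months and 6-months". On place, the section states: "Biometric, biomarker, and medication data will be collected by the study team at the Miller Center or biomarkers may be collected at a Geisinger lab". Biometrics are therefore taken at the Miller Center in both arms.

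On the classes, the Intervention part of Section 5.6 says: "meetings will be held in the evening and last approximately one to two hours". It adds: "Ten meetings will include a cooking demonstration and partaking in a meal prepared in the Cornerstone Kitchen". It does not say which ten of the 18 meetings these are.

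Section 5.6.1 puts randomisation at week 0 and the first measurements at week 1. Section 5.7 gives the primary clinical endpoint: "Clinical endpoint: Change in HbA1c at 6 months compared to baseline". Systolic pressure, BMI and waist belong to Specific Aim 1 (Section 4.2). Weight, BMI and blood pressure are secondary endpoints (Section 5.8).

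**The concern.** Weight, waist and blood pressure can vary with the hour, a recent meal and the setting of the reading. In the CHIP arm the baseline occasion is tied to an evening class and the 6-month occasion is not. In the control arm the type of occasion stays the same. Section 5.9.1 estimates the between-group difference in change, and a shift that enters one arm's baseline only does not cancel in that difference. Randomisation does not help, because the schedule itself depends on the arm.

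At stake are the 6-month estimates for the Aim 1 and secondary biometrics, which Section 5.9.1 carries forward to the design of a larger trial. The documents set no rule on time of day, meals or rest before a reading, and do not ask for clock time to be recorded. A shift of this kind could not be separated from a treatment effect afterwards.

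**Working it through.** **Inputs.** From the documents: 30 per group and 95% half-widths of 0.37 and 0.52 SD of the change (Section 5.9.2); the collection occasions (Section 5.6); the visit weeks (Section 5.6.1). Not in the documents, so assumed below: the size of any class effect and the SD of change for the biometrics.

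**1. The plan's own precision.** One arm: t(0.975, 29)/√30 = 0.373. Difference: t(0.975, 58) × √(2/30) = 0.517. Both agree with the stated figures. The standard error of the difference is √(2/30) = 0.258 SD.

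**2. Occasions side by side.**

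| Visit | CHIP | Control |
|---|---|---|
| Baseline (week 1) | At the first class (overview); appointments before or after it (detailed text) | Private appointment |
| 3 months (week 12) | At the last class (overview); that week (detailed text) | Private appointment |
| 6 months (week 26) | Individual appointment | Private appointment |

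**3. What enters the difference in change.** Let c be the mean shift of a class-linked reading relative to an appointment reading. Let f be the share of CHIP baselines affected and g the share of CHIP 3-month readings affected. Take control conditions as constant.

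- 6 months: bias = 0 − f·c = −f·c.
- 3 months: bias = g·c − f·c = (g − f)·c, which is zero when g = f.
- Baseline before randomisation: the baseline term is then the same in both arms. Bias at 6 months = −f·c − (−f·c) = 0. Bias at 3 months = (g·c − f·c) − (−f·c) = g·c.

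The 6-month problem thus comes from taking baseline after allocation. If class readings run high (c > 0), CHIP looks better at 6 months; if they run low, it looks worse.

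**4. Consequence for the interval.** For a net shift b = f·c in SDs of the change, coverage comes from the noncentral t distribution with 58 df and noncentrality b/0.258.

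| Assumed net shift (SD) | Share of the half-width | Coverage of the nominal 95% interval |
|---|---|---|
| 0.05 | 10% | 94.6% |
| 0.1 | 19% | 93.3% |
| 0.2 | 39% | 88.1% |
| 0.3 | 58% | 79.2% |

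**5. Illustration for systolic pressure.** Assume an SD of change of 10 to 20 mmHg, so the half-width is 5.17 to 10.34 mmHg. A net shift of 2 mmHg gives coverage of 88.1% to 93.3%; a net shift of 5 mmHg gives 52.2% to 84.1%. Dilution matters: a 4 mmHg class effect in half of the baselines is a net shift of 0.5 × 4 = 2 mmHg.

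**6. Effect on the SD of change.** Mixing conditions within the CHIP arm adds f(1 − f)c² to the variance. With f = 0.5 and c = 0.5 SD this is 0.25 × 0.25 = 0.0625, so the SD rises by a factor √1.0625 = 1.03. The variability estimate is little affected; the exposure is in the mean.

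**The case against.** The strongest reply is that the contrast is softer than the overview sentence suggests. The detailed text calls the CHIP baselines appointments, allows them before class, and gives a week for the 3-month readings. Both arms are measured at one site, with the same measures and protocols promised. This stands in part. It dilutes any shift, so the full class effect is only an upper bound. It does not remove the asymmetry: post-class baselines remain open to one arm only, and no written procedure shows what the shared protocols cover.

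A reader might infer more than the documents support:

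- *That CHIP readings are evening readings and control readings daytime ones.* Only the classes have a stated time of day. Control and 6-month visits have none and could also be in the evening. Nothing holds a control's hour constant across visits either.
- *That CHIP readings follow a meal.* No meal is documented at the first or last class.
- *That the artefact favours CHIP.* The sign of c is unknown.
- *That the 6-month problem would persist with a baseline taken before randomisation.* It would not. The baseline occasion could then not differ by arm, and Section 5.6 gives all participants 6-month appointments. Only the 3-month comparison would remain exposed.
- *That the primary clinical result is compromised.* HbA1c is a laboratory test and is little affected, as is LDL-C.

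**Conclusion.** The point holds as a possible bias, not a demonstrated one. The occasion of measurement depends on arm at baseline and at 3 months, and an effect of setting, hour or recent meal on weight, BMI, waist or blood pressure would enter the 6-month difference in change. A constant class effect largely cancels in the 3-month change.

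The documents fix neither size nor direction. A net shift of 0.1 SD or less would be minor against a half-width of 0.52 SD; 0.3 SD would not be. Those figures rest on assumed shifts, constant control conditions and 30 analysed per group. No sample-size figure changes. Severity is minor; the change is worth making because it is cheap.

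**What to change.** - Reconcile the overview and the detailed text in Section 5.6 on when CHIP-arm biometrics are taken.
- Write one measurement procedure for weight, waist and blood pressure, and apply it to both arms at baseline, week 12 and week 26.
- On class days, measure CHIP participants before the class and before any meal, after seated rest. Drop the post-class option for biometrics.
- Offer both arms the same time band, including early evening so that CHIP participants need no extra trip. Keep each participant's three visits in the same part of the day.
- Record clock time and time since the last meal at every visit in both arms.

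Moving baseline ahead of randomisation would by itself remove the 6-month problem, but would leave the 3-month comparison exposed unless week 12 is standardised too.

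The cost is protocol wording, some scheduling effort, and earlier arrival for CHIP participants on up to two class days. It needs no added visits or participants.

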5.6.1 Study Time and Events Table

Intervention Arm

Week	CHIP Program: 2 classes per week							CHIP Program: 1 class per week							26	52
	0	1	2	3	4	5	6	7	8	9	10	11	12			
Consent	X															
Randomization	X															
CHIP Program		P	P	P	P	P	P	H	H	H	H	H	H	H	P	
Height		X														
Weight		X													X X	
Waist circumference		X													X X	
Blood Pressure		X													X X	
HbA1c		X													X X	
Cholesterol		X													X X	
Wellbeing360 Survey		X													X X	
Satisfaction Survey															X X	

P = in person H = Hybrid (in-person/online)

Control Arm

Week	0	1	12	26
Consent	X			
Randomization	X			
Height		X		
Weight		X	X	X
Waist circumference		X	X	X
Blood Pressure		X	X	X
HbA1c		X	X	X
Cholesterol		X	X	X
Wellbeing360 Survey		X	X	X

5.7 Primary Endpoints

Clinical endpoint: Change in HbA1c at 6 months compared to baseline.

Feasibility endpoint: What proportion of individuals contacted agree to participate; what proportion of participants complete the intervention; what proportion of individuals contacted are excluded from the study based on lack of access to transportation or internet.

5.8 Secondary Endpoints

- HbA1c control at 3 months
- LDL-C at 3 and 6 months
- Biometrics at 3 and 6 months: weight, body mass index, blood pressure
- Psychosocial/behavioral: Wellbeing360 at 3 and 6 months
- Health behaviors, as measured by CHIP participation: overall program completion, attendance stratified by in-person versus online, proportion of required in-person visits attended
- Number of diabetes medications prescribed at 3 and 6 months
- Total cost of care over 6 months and comparison of total cost of care over the same 6 months the year prior and the 6 months immediately leading up to the study start date.

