population scale implementation of CHIP intended to improve the overall health and total cost of care of high-risk individuals such as patients with T2DM. Specifically, both the Vanderbilt and Ohio University studies addressing ROI are pilot scale and appear to lack rigorous randomized control groups, thus making them subject to selection bias. Both of these studies rely upon combinations of pre-post comparisons and comparisons between presumably motivated intervention groups that were actively enrolled in CHIP versus non-randomized, observational health plan member controls, which likely represents a less motivated population (Remy et al. 2017, 293-300; Anonymous; Drozek 2020). The lack of true randomization casts doubt upon the scale of ROI reported by Vanderbilt and ROI which may ultimately be reported by Ohio University. Unfortunately, implementing CHIP requires various licensing fees and per participant charges paid to the Lifestyle Medicine Institute, in addition to the local costs of administering the program. Even at large scale, CHIP can be expected to cost at least \$300-\$500 per participant. Due to this significant cost, it is imperative to rigorously evaluate the clinical and financial ROI of CHIP before implementing it at a population scale. Finally, to our knowledge there has never been a flexible online/in person application of CHIP. This could be an effective tool to bring CHIP to rural populations and might prove of general use in this era of uncertainty related to pandemics, climate events and other disruptions.

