4 HYPOTHESIS AND SPECIFIC AIMS

4.1 Hypothesis

Geisinger Health Plan members with T2DM offered CHIP in addition to standard insurance coverage will have improvement in HbA1c and improvements in other biometrics, biomarkers, psychometrics and utilization/financial outcomes, including LDL-C, systolic blood pressure, body mass index, waist circumference, number of diabetes medications prescribed, Wellbeing360 survey, and total cost of healthcare.

4.2 Specific Aim 1

To compare change in HbA1c, LDL-C, systolic blood pressure, body mass index, and waist circumference for GHP members offered CHIP versus members offered standard insurance coverage at 3- and 6-months.

4.3 Specific Aim 2

To compare number of diabetes drugs prescribed and total health care costs of GHP members offered CHIP versus GHP members offered standard insurance coverage at 3- and 6-months.

4.4 Specific Aim 3

To compare change in responses on the Wellbeing360 survey of GHP member offered CHIP versus employees offered standard employee wellness options

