5.9.1 Statistical Analysis Plan

Randomization scheme: The randomization scheme will be stratified on the potential study participant's most recent HbA1c value (< 6.5% vs \geq 6.5%).

Analysis methods: Descriptive statistics and plots for each variable will be inspected to identify influential points and to assess normality. Non-normally distributed variables will be transformed (e.g., logarithmic) as appropriate for parametric analysis, otherwise non-parametric methods will be used. Means, standard deviations, medians, ranges (maximum/interquartile) and 95%

confidence levels will be calculated for baseline outcome variables (HbA1c, LDL-C, systolic blood pressure) for the entire group, and stratified by CHIP vs. control group. The difference in outcomes will be calculated and treated as dependent variables. Since this is a pilot study the focus of the analysis will be estimating the mean and standard deviation of the change at 3- and 6-month for each primary and secondary outcome. We will also estimate the difference of the changes between groups and the variability. These estimates will then be used to design a larger scale study that will seek external funding. All estimates will be calculated under the ‘intent-to-treat’ principle. We will also collect and report on the proportion of individuals contacted and consent to participate, and compliance on attending the CHIP session. For those individuals contacted and do not agree to participate, we will collect the reason (e.g., not interested, lack of access to transportation, lack of internet, not able to reach).

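### The cost endpoint has two unranked pre-study baselines, and its within-arm changes compare windows with unequal claims run-out; the randomised contrast should be named as the estimand

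*Combined protocol and SAP*

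**What the plan says.** Section 5.8 gives the cost endpoint as a six-month total, together with a "comparison of total cost of care over the same 6 months the year prior and the 6 months immediately leading up" to the start of the study. It does not say which earlier window leads. It does not state a between-arm comparison either, but nor does any other entry in that list.

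The contrast is set elsewhere. Specific Aim 2 (section 4.3) is "To compare number of diabetes drugs prescribed and total health care costs of GHP members offered CHIP versus GHP members offered standard insurance coverage". Section 5.9.1 puts the focus on "estimating the mean and standard deviation of the change at 3- and 6-month for each primary and secondary outcome", and then adds: "We will also estimate the difference of the changes between groups and the variability". Estimates follow intention to treat.

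On timing, section 5.5.2 allows "a 3-month lag in claims data processing" after 12 + 14 = 26 weeks of intervention and follow-up, then 3 months for retrieval and analysis, within about 15 months in all. Inclusion criterion 1 (section 5.2.2) requires a full year of plan membership before enrolment. Nothing in the documents sets a common run-out for the three windows, a completion factor, or any handling of season.

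**The concern.** There are two separate problems.

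- **Two baselines.** With two unranked windows, every member has two cost changes. This reaches the randomised comparison as well: the difference of changes has two values and two SDs, and no rule says which one informs the design of the larger study. Supplying that design is the stated purpose of the estimates.
- **Unlike windows.** The within-arm mean change sets recent claims against claims that have had much longer to arrive. For one of the two windows it also sets one half of the year against the other. A fall in cost could then show in either arm with no effect of CHIP.

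The second problem matters because section 3 treats return on investment as the open question for a payer. It faults two earlier CHIP evaluations in these terms: "Both of these studies rely upon combinations of pre-post comparisons". A within-arm cost change reported without qualification would invite the same reading.

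**Working it through.** **1. The plan's own precision figures (section 5.9.2).** With 30 per arm and two-sided 95% t intervals:
- Within arm: t(0.975, 29)/√30 = 2.045/5.477 = 0.373, stated as 0.37.
- Between arms: t(0.975, 58) × √(2/30) = 2.002 × 0.2582 = 0.517, stated as 0.52.

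Both reproduce. Both are in units of the SD of the change, and cost has two such SDs. Required sample size scales with SD². If costs in the windows have equal variance σ² and pre-study window k has correlation r_k with the study window, then SD_k² = 2σ²(1 − r_k). The two planning sample sizes are in the ratio (1 − r_1)/(1 − r_2). The documents give no correlation, so the gap cannot be sized.

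**2. Claims run-out.** Put study start at month 0. The study window ends at month 6 and the claims cut is at 6 + 3 = month 9.

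| Window | Months | Run-out by service date | Mean |
|---|---|---|---|
| Study | 0 to 6 | 3 to 9 | 6 |
| Just before | −6 to 0 | 9 to 15 | 12 |
| Prior year | −12 to −6 | 15 to 21 | 18 |

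The minimum run-outs are 3, 9 and 15 months. A later cut would lengthen all three equally, so the gaps of 6 and 12 months do not depend on the cut date.

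**3. Season.** The prior-year window covers the same calendar months as the study window and is season-matched. The just-before window is the opposite half of the year. The 15-month timeline leaves about 15 − 6 − 3 − 3 = 3 months for recruitment and start-up, so members start close together and season would not average out.

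**4. Within-arm change with no CHIP effect.** Let c be the share of study-window cost visible at the cut, with earlier windows taken as complete, and s the ratio of study-season to opposite-season cost. Both are assumptions.
- Against the prior year, the apparent change is c − 1: −2% at c = 0.98, −5% at 0.95, −6% at 0.94.
- Against the window just before, it is c × s − 1. At c = 0.95 this is 0.95 × 0.9 − 1 = −14.5% for s = 0.9, and 0.95 × 1.1 − 1 = +4.5% for s = 1.1.

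For scale, section 3 expects the program to cost at least $300-$500 per participant. A 6% shortfall equals $300 when true six-month cost is 300/0.06 = $5,000; a 2% shortfall equals it at 300/0.02 = $15,000. The documents give no cost level.

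**5. Between-arm difference of changes.** The factors c and s apply to both arms, so with no CHIP effect the expected difference is zero. A simulation with 30 per arm, skewed and correlated costs, no CHIP effect, c from 0.90 to 1 and s of 0.9, 1 or 1.1 agrees. Over 24 comparisons the mean between-arm difference was never more than 0.7% of mean six-month cost (about two simulation standard errors), and a 5% test rejected in 3.8% to 4.8% of runs. A true CHIP effect on cost would be shrunk by the factor c, so by 5% at c = 0.95.

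**6. Adjustment against change scores.** For one baseline window with equal variances and pre-post correlation r, the per-member variance is 2σ²(1 − r) for the change and σ²(1 − r²) after adjustment. The ratio is (1 + r)/2, rising from 1/2 at r = 0 towards 1 as r approaches 1. If all three windows have equal variance and common correlation r, adjusting for the 12-month total leaves σ²(1 − r)(1 + 2r)/(1 + r). Against a single-window change the ratio is then (1 + 2r)/(2(1 + r)), from 1/2 to 3/4. These ratios ignore the small loss from estimating one slope.

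**The case against.** The strongest reply is that the plan already has the protection it needs. Section 5.8 is a list of variables, section 5.1 describes a randomised comparison of financial outcomes, Aim 2 sets CHIP against standard coverage, and 5.9.1 commits to a difference of changes. Anything common to both arms cancels there, and a control arm showing the same fall would expose the artefact. Section 3's criticism of earlier studies is also tied to their lack of randomisation, which this trial does not share. All of this stands.

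It is also fair that the plan builds in a claims lag and that nothing shows 3 months to be too short. Nor is the direction of the just-before comparison known, since season may outweigh run-out. Finally, the within-arm interval is wide: a 6% shortfall exceeds its half-width only if the SD of the cost change is below 0.06/0.37 = 16% of mean cost. That stands too, although a shift with the same sign in both arms is bias and not noise.

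The reply does not settle the choice of baseline. The difference of changes is unbiased against either window, but the two give different estimates and different SDs, and the plan would carry both forward. Nor does it cover the within-arm changes, which 5.9.1 makes the focus.

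**Conclusion.** The point holds in a limited form. Section 5.8 leaves the cost change doubly defined. The within-arm changes mix minimum run-outs of 3, 9 and 15 months, and one of them also mixes seasons. The run-out effect alone is an apparent saving of about 2-6% in each arm, on the assumption that 94-98% of study-window cost is visible at the cut and the earlier windows are complete. The seasonal effect has unknown sign and applies only to the just-before window.

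A reader might infer that the cost endpoint is nothing but a before-after comparison, or that the trial would show a false saving for CHIP over control. The documents do not support either reading: sections 4.3 and 5.9.1 plan the randomised contrast, and the artefact cancels in it on average. A reader might also infer that claims are badly incomplete at 3 months, but no passage gives a completeness rate.

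**What to change.** In sections 5.8 and 5.9.1, state the cost estimand as the CHIP-minus-control difference in mean total cost over the six-month study window, adjusted for each member's total cost in the 12 months before the study start date. That covariate is the two existing windows combined, so it removes the choice between them and spans both halves of the year. It replaces the two change scores and, under the equal-variance conditions shown, has no larger variance than a change score. Section 5.8 counts from study start while inclusion criterion 1 counts from enrolment, so use one anchor date, defined identically in both arms, for every window.

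Report within-arm before-after cost changes as descriptive only, and not as savings or return on investment. In those comparisons, count a claim only if it was processed within 3 months of the end of its window. The between-arm estimate does not need this filter.

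The cost is a few lines of text and one filter. Claim processing dates must be in the data pull; section 5.10.1 mentions relevant dates without naming these. A few late-processed claims drop out of the descriptive pre-study totals.
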